	 Begin/continue maximum supportive care and adequate combination anti-emetic treatments (see Section 7.6.1 for guidance on avoiding QT-prolonging concomitant medication). Consider gastroenterology consult;
	 Hold both rociletinib and MPDL3280A until < Grade 1. Restart rociletinib at next lower dose. If no recurrent symptoms, restart MPDL3280A;
	• If Grade \geq 3 nausea/vomiting recurs, MPDL3280A should be discontinued.

Toxicity	Attribution to both agents
Ocular Toxicity:	Grade ≥ 2:
	 Hold both study drugs until < Grade 1 (dose delays longer than 14 days require discussion with the Medical Monitor);
	 Obtain ophthalmology consult; uveitis or episcleritis may be treated with topical corticosteroid eye drops;
	 Reintroduce rociletinib at a reduced dose when symptoms resolved to Grade ≤ 1. If no recurrent symptoms, restart MPDL3280A; MPDL3280A should be permanently discontinued for immune-mediated ocular disease that is unresponsive to local immunosuppressive therapy.
Laboratory abnormalities	Grade \geq 3 Laboratory abnormalities related to study drug that are asymptomatic and deemed by the Investigator not to be clinically significant
	 After discussion between Investigator and Medical Monitor, rociletinib dosing may be delayed, and treatment subsequently resumed at the current dose level or at a reduced dose. If abnormality persists > 7 days, MPDL3280A dosing may also be held and subsequently resumed at the same dose level when toxicity resolves to baseline grade plus one.
Liver toxicities	Grade \geq 3 AST, ALT, or bilirubin abnormalities (or AST or ALT \geq 10 × ULN in patients with hepatic metastases) related to study drug that are asymptomatic and deemed by the Investigator not to be clinically significant
	• Hold both study drugs until recovery Grade ≤ 1 ;
	 Initiate systemic steroids IV for 48 hours followed by oral taper;
	 Monitor LFTs QOD until decreasing, then weekly;
	 If resolved to baseline grade plus one (eg, if baseline Grade 1, then Grade 2) resume MPDL3280A dosing;
	 If AE persists permanently discontinue MPDL3280A.
Other Grade ≥ 3 non-hematologic or Grade 4	 Hold rociletinib and MPDL3280A until recovery to Grade ≤ 1 and then restart rociletinib at a reduced dose and MPDL3280A at the same dose.
hematologic toxicity	 If the Grade 4 AE recurs (a second time), then MPDL3280A should be discontinued.
	 If the Grade 4 AE recurs (a third time), then rociletinib should be discontinued.

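### Table 18's liver row directs steroids and a stop for persistence only for asymptomatic, non-significant Grade ≥3 events; symptomatic or significant ones get weaker written instructions

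*Combined protocol and SAP*

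**What the plan says.** Table 18 (Section 6.3) covers toxicity attributed to both agents. Its liver row applies to Grade ≥3 AST, ALT or bilirubin abnormalities, with a separate transaminase criterion for some patients (at least 10 × ULN). The trigger then ends with a qualifier: "in patients with hepatic metastases) related to study drug that are asymptomatic and deemed by the Investigator not to be clinically significant". The row first holds both drugs to Grade ≤1. On steroids its instruction is "Initiate systemic steroids IV for 48 hours followed by oral taper". For monitoring, the site is told "Monitor LFTs QOD until decreasing, then weekly". The rule for going back on MPDL3280A is "If resolved to baseline grade plus one (eg, if baseline Grade 1, then Grade 2) resume MPDL3280A dosing", while the stopping rule is "If AE persists permanently discontinue MPDL3280A".

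No Table 18 row names symptomatic or clinically significant liver events. The row they fit is the one for other Grade ≥3 non-hematologic toxicity. Its hold instruction begins "Hold rociletinib and MPDL3280A until recovery to Grade", with 1 as the ceiling. The restart rule is "then restart rociletinib at a reduced dose and MPDL3280A at the same dose". Its stops depend on recurrence: "If the Grade 4 AE recurs (a second time), then MPDL3280A should be discontinued", and a third occurrence stops rociletinib.

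Section 6.2.3 sends all LFT abnormalities to Table 13, whatever the symptoms. Section 6.2 permits, but does not direct, corticosteroids for severe immune-related toxicity.

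**The concern.** Read literally, a site must start IV steroids for a hepatic abnormality that the investigator considers unimportant. If the patient has symptoms, or the investigator judges the event significant, no table directs steroids and no table stops MPDL3280A because the event persists. The two conditions are joined, so an asymptomatic event judged significant also leaves the row.

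This runs against the protocol's own ranking of severity. In Section 3.2.1, symptomatic Grade ≥3 hepatic toxicity becomes a DLT after 48 hours, asymptomatic only after 7 days. In Table 18's amylase/lipase row, prednisone 10 mg is optional for asymptomatic Grade 4 elevations, while 60 mg/day is directed for symptomatic ones.

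At stake are patient safety and consistent management across about 14 sites. Section 6.2.3 itself says that immune-mediated hepatitis has been associated with MPDL3280A. The response-rate analysis is not affected.

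**Working it through.** No sample-size or error-rate arithmetic applies. The check sets the three sources side by side for a drug-related Grade ≥3 hepatic event attributed to both agents.

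| Instruction | Table 18 liver row (asymptomatic and not significant) | Table 18 'Other' row (symptomatic or significant) | Table 13 (any LFT abnormality) |
|---|---|---|---|
| Hold | Both drugs to Grade ≤1 | Both drugs to Grade ≤1 | MPDL3280A held at the two higher thresholds; continued in the middle band |
| Steroids | Directed | None named | Optional at the two higher thresholds; none named in the middle band |
| LFTs | Every other day, then weekly | None named | Every 48–72 hours, then weekly, at the two higher thresholds; at least weekly in the middle band |
| Permanent MPDL3280A stop | If the event persists | Second occurrence of a Grade 4 event | Life-threatening immune-related event |
| MPDL3280A resume | Baseline grade plus one | Grade ≤1, same dose | AST/ALT ≤3 × ULN, bilirubin <2 × ULN, prednisone ≤10 mg/day, Medical Monitor discussion |
| Rociletinib restart dose | Not stated | Reduced | Not addressed |

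The two higher thresholds are AST/ALT >10 × ULN, and AST/ALT ≥3 × ULN with bilirubin >2 × ULN. The middle band is AST/ALT >3 to <10 × ULN with bilirubin <2 × ULN.

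**Steroids.** The only directive liver steroid instruction sits in the first column. For symptomatic or significant events the firmest text is Table 13's option, and in the middle band there is not even that.

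**Stop for persistence.** It too appears only in the first column. Sections 5.7.4 and 11.1 limit holds to 14 days for rociletinib and 42 days for MPDL3280A, after which all study treatment stops, unless the Medical Monitor permits longer. That is a partial substitute.

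**LFT monitoring.** Every other day is every 48 hours, so Table 13's 48–72 hours nearly matches at the higher thresholds. The difference lies mainly in the middle band. Table 13's categories are all defined by AST/ALT, so an isolated bilirubin rise also has no entry there.

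**Middle-band conflict.** Table 13 continues MPDL3280A. Both Table 18 rows hold it for any Grade 3 event in that band. Section 6 says to modify doses by attribution, but no text says how the two tables combine.

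**Two secondary defects.**

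- The same asymptomatic liver abnormality also meets the laboratory row directly above. There rociletinib may be delayed after discussion, and MPDL3280A may be held only once the abnormality has lasted more than 7 days. The liver row holds both at once.
- In the liver row, with a normal baseline (Grade 0), baseline plus one is 0 + 1 = Grade 1, which agrees with holding to Grade ≤1. With a Grade 1 baseline it is 1 + 1 = Grade 2, which does not. Section 4.2 allows raised baselines: AST/ALT up to 2.5 × ULN (5 × ULN with liver metastases) and bilirubin up to 2.0 × ULN.

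**The case against.** The strongest reply is that a site following the whole protocol would not neglect a symptomatic hepatic event. Both drugs are held under the 'Other' row. Section 6.2.3 requires immediate LFTs, reviewed before the next dose, for right upper-quadrant pain or unexplained nausea or vomiting. Section 6.2 calls for standard medical practice and allows steroids. Section 11.1 ends treatment for any event that the investigator considers an unacceptable safety risk, and Section 9.6 makes hepatitis and marked transaminitis events of special interest. All of this stands and limits the consequence. It does not supply a directive steroid instruction or a stop for persistence.

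A reader might infer that symptomatic events leave treatment running, that steroids are withheld from these patients, or that liver-test monitoring is lost along with the other two instructions. The documents do not support any of these. The hold is the same in both rows, steroids remain available, and Table 13 covers most of the monitoring.

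It can also be said that a row naming AST, ALT and bilirubin naturally prevails over a generic laboratory row. That is the likelier reading, so the overlap is minor, though no rule states it. Lastly, the liver row gives no time limit for persistence, so the instruction that symptomatic patients miss is itself loosely defined. That is fair, but it does not justify reserving it for milder events.

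**Conclusion.** The point holds in a limited form. Two instructions, directive IV steroids and the permanent MPDL3280A stop for persistence, attach to the milder hepatic events and not to the symptomatic or clinically significant ones. A narrower contradiction exists in Table 13's middle band, where one table continues MPDL3280A and the other holds it. The laboratory-row overlap and the resume conflict, which needs a raised baseline, are secondary.

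The conclusion rests on reading the liver row's qualifier as written. The laboratory row above uses the same qualifier, so it may have been carried over; that is an inference. Whether a given middle-band value is Grade 3 depends on CTCAE v4.03 limits, which the protocol cites but does not reproduce. The documents give no rate of Grade ≥3 hepatic events for the combination, so the size is one of wording and consistency, not of patients affected. It should be corrected, but it is not a reason to doubt the design.

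**What to change.** 1. In the liver row, delete the restriction to events that are asymptomatic and judged not clinically significant, so that it covers all Grade ≥3 drug-related AST, ALT or bilirubin events.
2. In the laboratory row, add: other than AST, ALT or bilirubin.
3. For all events in the liver row, use one resume threshold, that of Section 5.7.4: Grade 1, or the baseline level if baseline was above Grade 1. Restart rociletinib at a reduced dose, and carry over the 'Other' row's Grade 4 recurrence stops.
4. State that, for events attributed to both drugs, Table 18 governs drug holds and steroid initiation, while Table 13's MPDL3280A restart limits, hepatologist consult, second-line immunosuppression and life-threatening stop also apply.

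The same edit could define how long an event must last to count as persistent.

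The cost is protocol wording and site notification. Steroids become directive for more hepatic events; Section 7.4 notes that they may attenuate MPDL3280A's benefit and prefers alternatives where feasible. Restarts become somewhat more conservative. A patient with liver metastases whose baseline AST/ALT is between 3 and 5 × ULN could not meet Table 13's restart limit, but that limit already applies.

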6.3 Overlapping Expected or Potential Toxicities

Guidelines for the management of specific expected or potential overlapping toxicities for rociletinib and MPDL3280A are described in Table 18.

Table 18:Management of Overlapping Toxicities

Toxicity	Attribution to both agents
Rash/Skin Toxicity:	Grade 2: continue both agents; initiate supportive care.
	Grade 3:
	 Obtain dermatology consult;
	■ Hold rociletinib and MPDL3280A until resolved to ≤ Grade 1, then reinitiate rociletinib at a dose agreed upon with the Sponsor's Medical Monitor; (dose delays longer than 14 days also require discussion with the Medical Monitor);
	 Restart MPDL3280A if rash does not occur within 14 days of rociletinib re-initiation;
	 Hold rociletinib and permanently discontinue MPDL3280A if the patient experiences recurrent Grade ≥ 3 skin toxicity. When rash is Grade 1, restart rociletinib at previous dose. If Grade ≥ 3 rash recurs, rociletinib should be discontinued permanently.
	Grade 4 : Permanently discontinue MPDL3280A. Hold rociletinib until rash is Grade 1 and restart at one dose level lower (dose delays longer than 14 days require discussion with the Medical Monitor). If Grade \geq 3 rash recurs, rociletinib should
	be discontinued.
Diarrhea:	Grade 2 : Supportive care unless > 48 to 72 hrs. Then reduce dose of rociletinib and hold MPDL3280A until resolves to < Grade 1.
	Grade 3 : Hold rociletinib and MPDL3280A Obtain gastroenterology consult, discontinue NSAIDs or medications known to exacerbate colitis, Initiate steroid treatment. If resolves to < Grade 1, then restart rociletinib at next lower dose. If no recurrent symptoms, within 14 days resume MPDL3280A as long as steroid dose is ≤ 10 mg oral prednisone equivalent per day (dose delays longer than 14 days require discussion with the Medical Monitor).
	Grade 4 : MPDL3280A should be permanently discontinued. Hold rociletinib until diarrhea is Grade 1 and restart at one dose level lower. If Grade \geq 3 diarrhea recurs, rociletinib should be permanently discontinued (dose delays longer than 14 days require discussion with the Medical Monitor).
Nausea/Vomiting:	Grade1-2: Continue treatment. Begin maximum supportive care and adequate anti-emetic treatments (see Section 7.6.1 for guidance on avoiding QT-prolonging concomitant medication).
	Grade ≥ 3:

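### In the Table 18 liver row, a patient with baseline Grade 1 who has recovered to Grade 2 is told both to hold and to resume MPDL3280A

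*Combined protocol and SAP*

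**What the plan says.** Table 18 in Section 6.3 covers toxicities attributed to both agents. Its liver row applies to Grade 3 or higher AST, ALT or bilirubin abnormalities, with a separate AST/ALT threshold of 10 × ULN "in patients with hepatic metastases) related to study drug that are asymptomatic and deemed by the Investigator not to be clinically significant". Three of its bullets matter here.

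- First bullet: "Hold both study drugs until recovery Grade" 1 or lower.
- Second bullet: "Initiate systemic steroids IV for 48 hours followed by oral taper".
- Fourth bullet: "If resolved to baseline grade plus one (eg, if baseline Grade 1, then Grade 2) resume MPDL3280A dosing".

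The row has no separate restart instruction for rociletinib, and no wording that ranks the first bullet against the fourth.

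The Laboratory abnormalities row just above has a similar entry condition: "Laboratory abnormalities related to study drug that are asymptomatic and deemed by the Investigator not to be clinically significant". There, if the abnormality lasts more than 7 days, "MPDL3280A dosing may also be held and subsequently resumed at the same dose level when toxicity resolves to" baseline grade plus one. That row contains no competing Grade 1 hold.

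**The concern.** The first bullet names both drugs, so it covers MPDL3280A. The fourth releases MPDL3280A at a threshold that depends on baseline and can be higher. Its own worked example, baseline Grade 1 and restart at Grade 2, is a case in which the first bullet still requires a hold. Two sites could take opposite actions for the same patient and both be following the protocol.

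The case can arise, because Section 4.2 admits patients with AST/ALT up to 2.5 × ULN, or 5 × ULN with liver metastases.

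What is at stake is when an antibody is given again after a liver abnormality that the row itself treats with intravenous steroids. Section 6.2.3 links MPDL3280A to immune-mediated hepatitis, and Section 6.2 notes that it has no antidote. The row's last bullet stops MPDL3280A permanently if the event persists, without a grade or a time. A patient who settles at Grade 2 has therefore resolved under one bullet and not recovered under the other.

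**Working it through.** No sample size, power or error rate is involved. The check compares the two thresholds and then asks how many doses the difference can affect.

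**Thresholds.** Let b be the baseline grade. The first bullet allows MPDL3280A at current grade ≤ 1. The fourth allows it at current grade ≤ b + 1.

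| Baseline grade b | First bullet | Fourth bullet (b + 1) | Gap | Grade at which both apply |
|---|---|---|---|---|
| 0 | ≤ 1 | ≤ 1 | 0 | none |
| 1 | ≤ 1 | ≤ 2 | 1 | Grade 2 |

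A patient who reaches Grade 1 or lower satisfies both bullets, so the conflict lasts only while a baseline Grade 1 patient is at Grade 2. The same formula gives a wider gap at higher baseline grades. The documents do not print the CTCAE liver cut-offs, so the point rests on baseline Grade 1, which is the row's own example.

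**Doses affected.** The inputs are in Section 5.7.4 (the limits are repeated in Section 11.1): rociletinib may be held for up to 14 days and MPDL3280A for up to 42 days. A longer hold needs the Medical Monitor's permission; otherwise all study treatment stops. MPDL3280A is given every 21 days.

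- On the MPDL3280A limit alone: 42 / 21 = 2 scheduled doses.
- At Grade 2, however, the first bullet also keeps rociletinib on hold whichever bullet governs MPDL3280A. The 14-day limit is therefore reached first. Since 14 < 21, that period contains at most one scheduled MPDL3280A dose. With the ±3-day visit window of Table 1, consecutive infusions could be as close as 21 − 3 − 3 = 15 days, still more than 14.

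**Does the rest of Table 18 settle the order?** Treating the fourth bullet as an MPDL3280A exception would restart the antibody while rociletinib is still held. Of the ten rows, six restart rociletinib first: rash, diarrhea, nausea/vomiting, ocular, pulmonary and amylase/lipase. The rash row says "Restart MPDL3280A if rash does not occur within 14 days of rociletinib re-initiation" and the nausea/vomiting row says "Restart rociletinib at next lower dose. If no recurrent symptoms, restart MPDL3280A". No other row states the reverse order. Against that, the Laboratory abnormalities row is the closest in kind and uses baseline plus one for MPDL3280A. The table points both ways.

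**The case against.** The strongest reply is that the fourth bullet is plainly the MPDL3280A rule. It is the only resume instruction in the row, it names MPDL3280A alone, and its example would be pointless if the first bullet governed that drug. The Laboratory abnormalities row supports it. The rows that restart rociletinib first mostly concern symptomatic toxicities. This is a well-supported way to resolve the conflict, but the row does not state it, and the first bullet expressly includes both drugs.

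It is also fair to say that Section 6 is framed as guidance, that liver tests under this row are repeated every other day until they fall, and that the group is small. These points lower the priority but do not remove the contradiction.

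A reader might infer three stronger things that the documents do not support.

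- *That Section 5.7.4 governs, so the fourth bullet is simply wrong.* Its Grade 1 (or baseline) threshold is written for toxicities equivalent to a DLT. Section 3.2.1 does list prolonged asymptomatic Grade 3 hepatic toxicity, but under an opening condition that the event be clinically significant. The liver row covers events judged not to be.
- *That restarting at Grade 2 is unsafe by the protocol's own standard.* Table 13 has strict restart conditions for AST/ALT above 10 × ULN, and for AST/ALT of at least 3 × ULN with bilirubin above 2 × ULN. It also continues MPDL3280A, with at least weekly tests, for AST/ALT above 3 and below 10 × ULN with bilirubin below 2 × ULN.
- *That two MPDL3280A doses are routinely at stake.* That uses only the 42-day limit and overlooks the concurrent rociletinib hold.

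**Conclusion.** The contradiction stands on the text. For a baseline Grade 1 patient at Grade 2, the row requires both holding and resuming MPDL3280A, and no wording gives precedence. The gap is one grade, and usually at most one scheduled dose is affected before the Medical Monitor is involved or all treatment stops. That figure assumes rociletinib remains on hold under the 14-day limit. It could be larger if a longer hold is permitted, or if rociletinib is stopped for toxicity and MPDL3280A continued alone, as Section 5.7.4 allows.

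The scope is narrow: attribution to both agents, no symptoms, and judged not clinically significant. The documents give no frequency for this. No endpoint or analysis is affected. The documents do not show which bullet is the right one, only that the row must choose. Priority is minor.

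**What to change.** State one MPDL3280A restart threshold in the liver row. Either option resolves the conflict:

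- **(a)** Limit the Grade 1 hold in the first bullet to rociletinib and label the fourth bullet as the MPDL3280A rule. This fits the worked example and the Laboratory abnormalities row.
- **(b)** Use Grade 1 or lower, or the baseline level if baseline was above Grade 1, in both bullets. This borrows Section 5.7.4 as a model for wording, not as the governing rule.

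In either case, add a sentence saying whether the Table 13 restart conditions apply to events managed under this row: Medical Monitor discussion, AST/ALT ≤ 3 × ULN, bilirubin < 2 × ULN, and steroid ≤ 10 mg prednisone equivalent per day. Section 6.2.3 sends patients with abnormal liver tests to Table 13 without limiting it by attribution, while the Table 18 row repeats none of those conditions. The sentence should take account of the Table 13 band in which MPDL3280A continues.

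The cost is a few lines of table wording. Under Section 12.7 an amendment needs IRB approval before implementation and goes to the regulators, so it is best included in the next one. Under (b), a few patients may have a longer MPDL3280A hold, which counts toward the 42-day limit.

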7 PRIOR AND CONCOMITANT THERAPIES

Concomitant therapy includes any prescription medications or over-the-counter preparations used by a patient between the 28 days prior to the first dose of study treatment through 28 days after the last dose of study treatment, or the date of administration of subsequent anticancer therapy, whichever is earlier. All concomitant medications should be reported to the Investigator and recorded on the appropriate eCRF.

7.1 Anticancer or Experimental Therapy

No other anticancer therapies (including chemotherapy, radiation, and hormonal treatment [except corticosteroids and megestrol acetate], antibody or other immunotherapy or other experimental drugs) of any kind will be permitted while the patient is participating in the study.

Palliative radiation therapy intended to provide relief of cancer-related symptoms is permitted while the patient is on study treatment with approval from the Sponsor's Medical Monitor. Treatment should be held while the patient is undergoing radiotherapy.

Additionally, a patient who continues treatment post-progression may undergo radiation or other procedures to specific lesions post-progression, if the patient continues to benefit from treatment overall. See Section 8.2.1 for more details.

7.2 Hematopoietic Growth Factors and Blood Products

Erythropoietin, darbepoetin alfa, and/or hematopoietic colony-stimulating factors for treatment of cytopenias should be administered according to institutional guidelines. Prophylactic use of these agents is not permitted.

Transfusion thresholds for blood product support will be in accordance with institutional guidelines.

